7.6.3 General Principles

A general description of the statistical methods to be used to analyze the efficacy and safety of KRN23 is outlined below. The analyses planned in this protocol will be expanded in the SAP to include detailed description of the analyses. The SAP will be finalized and approved prior to the database lock. Any deviations from the analyses described in the protocol and SAP will be noted in the final clinical study report.

The completeness of the data affects the integrity and accuracy of the final study analysis. Therefore, every effort will be made to ensure complete, accurate and timely data collection, and to avoid missing data. The procedures for handling missing, unused, or spurious data, along with the detailed method for analyses will be presented in the SAP.

The statistical analyses will be reported using summary tables, figures, and data listings. Descriptive statistics will be used to summarize the data. For continuous variables, the mean, standard deviation, median, quartile, minimum, and maximum will be provided. For discrete data, the frequency and percent distributions will be provided.

Full analysis set will include all randomized subjects who received at least 1 dose of assigned medication, and full analysis set will be used for both efficacy and safety analyses.

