7.6.4 Efficacy Endpoints and Analyses

The full analysis set will be used for efficacy analyses, and subjects will be analyzed by the randomized treatment group.

The primary efficacy endpoint will be tested to compare the mean RGI-C global score between the KRN23 and active control groups.

At the Week 40 Analysis (the primary efficacy analysis time point), the primary hypothesis of the primary endpoint is to test whether there is a difference between the KRN23 and active control groups in the mean RGI-C global scores at Week 40. An Analysis of Covariance (ANCOVA) model with treatment group adjusting for baseline rickets severity and age will be used to test this hypothesis at a 2-sided alpha level of 0.05. The proportion of RGI-C responder will be summarized for each treatment group.

At the Week 64 Analysis (secondary analysis), RGI-C global score over time will be analyzed using the repeat measurement model that includes treatment group, visit, treatment group by visit interaction, and adjusted for baseline rickets severity and age.

The change from baseline in RSS total score over time will be analyzed using the same method as that of the RGI-C score.

Analyses of other efficacy and PD measures will be performed at Week 40, Week 64/EOS I, and Week 140/EOS II. Endpoints will be summarized descriptively by each treatment group. Treatment comparison will be performed using the repeat measurement model including treatment group, visit, treatment group by visit interaction, adjusting for baseline age, rickets severity. Other baseline covariate may be considered for adjustment.

The SAP will provide additional details on the planned efficacy analyses.

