8 STATISTICAL METHODS AND ANALYSES

8.1 General Principles

The efficacy analyses will be based on the full analysis set. The PD analyses will be based on the PD analysis set. The safety analyses will be based on the safety analysis set. Statistical tests will be two-sided hypothesis tests performed at the 5% level of significance for main effects. Confidence intervals will be 2-sided 95% confidence intervals, which will be provided for both within group estimate and between group difference. P-values will be rounded to and displayed in three decimals. If a p-value less than 0.0001 occurs, it will be shown in tables as <.0001. There will be no multiplicity adjustments, or adjustments for multiple comparisons. Continuous variables will be summarized by number of subjects and mean, standard deviation/standard error (SD/SE), median, Q1, Q3, minimum, and maximum values. Categorical variables will be summarized by number and percentage of subjects.

If an outlier is identified and/or a pronounced non-normal probability distribution is found for the difference between the two treatment groups, then a non-parametric analysis corresponding to that of the parametric counterpart, e.g. the Wilcoxon rank test for median, will be performed and be considered as the primary analysis to assess the treatment difference between KRN23 and active control groups. Such a model violation may be identified by graphical methods, measures of non-normality (e.g., skewness, kurtosis) or other appropriate methods.

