8.5.3 Analysis of Primary Efficacy Endpoint

The primary efficacy endpoint will be tested to compare the mean RGI-C global score between the KRN23 and active control groups.

At Week 40 analysis, an Analysis of Covariance (ANCOVA) model will be applied on the RGI-C global score with treatment group and baseline age stratification factor as independent variables, baseline RSS total score as a continuous covariate. The stratification factor of baseline RSS total score will not be included in the model.

For RGI-C knee, wrist and lower limb deformity scores, a similar ANCOVA model will be applied with baseline RSS wrist score used in RGI-C wrist score modeling and baseline RSS knee score used in RGI-C knee score and lower limb deformity score modeling.

At Week 64 analysis, RGI-C (global, knee, wrist and long leg) scores over time including Week 40 will be analyzed using GEE model that includes treatment group, visit, treatment group by visit interaction, baseline age stratification factor as independent variables, baseline RSS total score as a continuous covariate. The stratification factor of baseline RSS total score will not be included in the model.

The estimated difference of RGI-C between KRN23 treatment and active control group will be provided along with 95% CI and p-value. The estimated RGI-C score and its 95% CI within individual treatment groups will also be provided. Descriptive statistics for all RGI-C scores will be provided in both continuous and categorical summary. Summary of abnormality at baseline and change in abnormality at Week 40 and Week 64 will also be provided. A listing of RGI-C scores will be provided for each subject. Graphic displays of RGI-C scores will also be provided over time by treatment group.

If subjects receive orthopedic surgeries before week 40 X-ray visit, a sensitivity analysis will be performed by excluding these subjects from week 40 and week 64 RGI-C analyses. If subjects receive orthopedic surgery after week 40 but before week 64 X-ray visit, a sensitivity analysis will be performed at week 64 RGI-C analysis, where the week 40 RGI-C data will be used to impute Week 64 data for these subjects.

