10 APPENDICES

APPENDIX 1 SUMMARY OF STATISTICAL ANALYSIS APPROACHES ON EFFICACY ENDPOINTS

Primary Efficacy Endpoint

Endpoint	Scale	Analysis populations	Comparisons	Data Time Points	Week 40 Analysis
RGI-C global score	Continuous	Full Analysis Set	KRN23 vs SOC	Baseline, Week 40	ANCOVA

Key Secondary Efficacy Endpoint(s)

Endpoints	Scale	Analysis populations	Comparisons	Data Time Points	Week 40 Analysis	Week 64 Analysis
RGI-C long leg score	Continuous	Full Analysis Set	KRN23 vs SOC	Baseline, Week 40, Week 64	ANCOVA	GEE
Change from baseline in Recumbent length/standing height Z score	Continuous	Full Analysis Set	KRN23 vs SOC	Baseline, Week 24, Week 40, Week 64	GEE	GEE
Change from baseline in RSS total score	Continuous	Full Analysis Set	KRN23 vs SOC	Baseline, Week 40, Week 64	ANCOVA	GEE
Change in serum phosphorus from baseline to mean post-baseline values	Continuous	PD Analysis Set	KRN23 vs SOC	Baseline, Week 1, Week 4, Week 8, Week 16, Week 24, Week 32, Week 40, Week 52, and Week 64	ANCOVA	ANCOVA
Change from baseline in ALP	Continuous	PD Analysis Set	KRN23 vs SOC	Baseline, Week 4, Week 8, Week 16, Week 24, Week 32, Week 40, Week 52 and Week 64	GEE	GEE

Other Secondary Efficacy Endpoint(s)

Endpoints	Scale	Analysis populations	Comparisons	Data Time Points	Week 40 Analysis	Week 64 Analysis
RGI-C responder	Binary	Full Analysis Set	KRN23 vs SOC	Baseline, Week 40, Week 64	Logistic Regression	Repeated Measures Logistic Regression
RGI-C knee and wrist scores	Continuous	Full Analysis Set	KRN23 vs SOC	Baseline, Week 40, Week 64	ANCOVA	GEE
Change from baseline in RSS knee and wrist scores	Continuous	Full Analysis Set	KRN23 vs SOC	Baseline, Week 40, Week 64	ANCOVA	GEE
Change from baseline in Growth velocity Z score	Continuous	Full Analysis Set	KRN23 vs SOC	Baseline, Week 40, Week 64	ANCOVA	ANCOVA
Change from baseline in PROMIS pain, fatigue and physical function scores	Continuous	Full Analysis Subset (Baseline age \geq 5 years)	KRN23 vs SOC	Baseline, Week 24, Week 40, Week 64	GEE	GEE
Change from baseline in FPS-R score	Continuous	Full Analysis Subset (Baseline age \geq 5 years)	KRN23 vs SOC	Baseline, Week 24, Week 40, Week 64	GEE	GEE
Change from baseline in 6MWT total distance and percent of predicted normal	Continuous	Full Analysis Subset (Baseline age \geq 5 years)	KRN23 vs SOC	Baseline, Week 24, Week 40, Week 64	GEE	GEE

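### SAP 8.1 lets an undefined outlier or non-normality check replace the Week 40 ANCOVA as primary, so the trial's one confirmatory test is not fixed in advance

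*SAP*

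**What the plan says.** Protocol 7.6.4 sets the primary hypothesis as "whether there is a difference between the KRN23 and active control groups in the mean RGI-C global scores at Week 40". The test it names is ANCOVA at the 5% level; its words are: "model with treatment group adjusting for baseline rickets severity and age will be used to test this hypothesis at a 2-sided alpha level". SAP 8.5.3 agrees for Week 40: "an Analysis of Covariance (ANCOVA) model will be applied on the RGI-C global score with treatment group and baseline age stratification factor", with baseline RSS total score entered as a continuous term. The table in SAP Appendix 1 lists ANCOVA as the only Week 40 analysis of this endpoint. The two-sample t-test in Protocol 7.6.1 and SAP 3.5 is used for sizing only.

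SAP 8.1 then sets a rule for all analyses. "If an outlier is identified and/or a pronounced non-normal probability distribution is found for the difference between the two treatment groups", a non-parametric analysis matching the parametric one "will be performed and be considered as the primary analysis to assess the treatment difference between KRN23 and active control groups". The Wilcoxon test is given as an example. The violation may be found by "graphical methods, measures of non-normality (e.g., skewness, kurtosis) or other appropriate methods".

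**The concern.** The Week 40 RGI-C comparison is the trial's single confirmatory test, and SAP 8.1 leaves its identity to a judgement made once outcome data exist. The RGI-C raters are blinded (Protocol 7.5.2.1, SAP 5.5), but neither document says that the people who check the distribution are. Protocol 7.6.3 says "The SAP will be finalized and approved prior to the database lock", which does not help here, because the open choice sits inside the finalized SAP.

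Three things are at stake: control of type I error if the choice is influenced by results; the adjustment for baseline RSS and age, which a plain Wilcoxon test drops; and the match to the protocol's hypothesis, which concerns means.

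**Working it through.** **1. Does the rule reach the primary endpoint?** SAP 8.1 lists no exception, and SAP 8.5.3 neither repeats nor disapplies it. The rule's only function is to displace a parametric analysis named for some endpoint. If naming ANCOVA in 8.5.3 were enough to switch it off, it could never operate.

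**2. What an analyst following 8.1 must still decide**
- What counts as an outlier or as pronounced non-normality. No cut-off is given, and the list of methods is open-ended.
- What to examine. A parallel-group trial has no per-subject treatment difference, so this could mean residuals, scores by arm or something else.
- Which test replaces ANCOVA. Wilcoxon is only an example, and a rank ANCOVA fits the wording equally well.
- Which estimate to report. SAP 8.5.3 promises a difference with a 95% CI, but 8.1 names no estimator after a switch.
- Who decides, when, and whether with treatment labels visible.

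**3. The plan's own figure.** From SAP 3.5: means 1.80 and 1.40, SD 0.50, two-sided alpha 0.05, 30 per group including 10% drop-out. Effect size = 0.40/0.50 = 0.8; noncentrality = 0.8 × √(n/2).
- n = 26 per group: 0.8 × √13 = 2.88, t-test power 80.8%. Then 26/0.9 = 28.9, so 29 per group or 58 in total, against the stated 60.
- n = 30 × 0.9 = 27 per group: 0.8 × √13.5 = 2.94, 52 df, power 82.2%.

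The stated 60 for about 80% power is reproduced.

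**4. Simulation of the switch.** From the plan: 27 per arm, SD 0.5, difference 0 or 0.40, scores in thirds (mean of three raters, SAP 5.5), and one third of subjects under 5 (20 of 60, Protocol 7.1). Assumed, because the documents give no figure: correlation of baseline RSS with outcome of 0, 0.3 or 0.5; age unrelated to outcome; and all trigger cut-offs. There were 10,000 null and 6,000 alternative trials per correlation. The Monte Carlo SE is √(0.05 × 0.95/10,000) = 0.2 points for type I error and √(0.8 × 0.2/6,000) = 0.5 points for power.

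How often a switch would fire under the null:

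| Trigger on ANCOVA residuals | Fires in |
|---|---|
| Shapiro-Wilk p < 0.05 | 5–9% |
| Any residual beyond 3 SD | 10% |
| Any residual outside 1.5-IQR boxplot limits | 41–42% |
| Any residual beyond 2.5 SD | 48–50% |

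The last row uses internally studentized residuals. The same 2.5 cut-off fires in about 38–39% of trials with raw residuals divided by the residual SD, and in about 63–65% with externally studentized residuals.

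Consequences, by RSS-outcome correlation:

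| | 0 | 0.3 | 0.5 |
|---|---|---|---|
| Type I error, better of ANCOVA and Wilcoxon | 6.1% | 6.7% | 7.5% |
| Type I error, rank ANCOVA also allowed | 6.6% | 7.2% | 8.2% |
| Type I error, switch only if a residual exceeds 2.5 SD and switching helps | 5.8% | 6.1% | 6.5% |
| Power, ANCOVA | 79.3% | 82.8% | 89.1% |
| Power, Wilcoxon without covariates | 78.6% | 79.3% | 78.1% |
| Power, rank ANCOVA | 77.4% | 81.4% | 86.9% |
| ANCOVA and Wilcoxon disagree, null | 2.3% | 3.5% | 4.8% |
| ANCOVA and Wilcoxon disagree, difference 0.40 | 6.1% | 9.1% | 14.4% |

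Any of the four triggers applied mechanically gives a type I error of 5.1–5.5%. A repeat run under the same assumptions gave 6.2/6.9/7.3%, 6.5/7.3/8.0% and 5.7/6.4/6.2% for the first three rows, and 5.0–5.3% for mechanical use.

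**5. A less favourable distribution.** With 5% poor responders added, three integer raters and no covariate effect, Shapiro-Wilk fires in 46% of null trials, |skewness| > 0.5 or |excess kurtosis| > 1 in 60%, and a raw residual beyond 2.5 SD in 78%. Here ANCOVA has 67.5% power and Wilcoxon 73.7%.

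**The case against.** - **The error inflation is small.** The top figures need an analyst who always takes the favourable test, whereas 8.1 allows a move only away from ANCOVA and only after a trigger. This stands: the scenario closest to the text gives 0.8 to 1.5 points above 5%. The larger figures are worst cases for the tests simulated.
- **The next sentence of 8.1 speaks of a model violation, which points to residuals.** That is a reasonable reading and narrows what is checked. It supplies neither a cut-off nor a type of residual, and the type alone moves the 2.5 SD trigger from about 38% to about 65%.
- **The natural counterpart of ANCOVA is a covariate-adjusted rank analysis.** On that reading the power loss is 1.9/1.4/2.2 points. But the only test 8.1 names is Wilcoxon, so the adjusted reading is not secured.
- **Readers would see both results.** SAP 8.5.3 promises the ANCOVA estimate unconditionally, and Protocol 7.6.3 requires deviations to be reported. That limits the practical harm. It does not settle which result is primary, and a switch under 8.1 would not be a deviation.
- **The score is bounded and only pronounced non-normality counts.** Both are true, but a single outlier is a separate and sufficient trigger.
- **The firing rates use the reviewer's own cut-offs.** They do. They illustrate how much is left open and are not properties of the plan.

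**Conclusion.** The concern holds. SAP 8.1 as written can replace the primary test, and the plan does not determine when or with what.

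If the choice followed the results, type I error would exceed 5% by about 1 to 3 points (6.1% to 8.2%). With one trigger fixed beforehand and applied mechanically, it stays near 5%. An unadjusted Wilcoxon test costs 0.7 to about 11 points of power relative to ANCOVA as the assumed RSS-outcome correlation rises from 0 to 0.5, but its power stays at 78–79%, close to plan. These figures rest on 27 evaluable subjects per arm, near-normal scores in thirds, and assumed correlations and cut-offs.

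This is a pre-specification gap that should be fixed. It is not a threat to the sample size or an argument against rank methods.

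**What to change.** In SAP 8.5.3, add one sentence: the ANCOVA described there is the primary analysis of the Week 40 RGI-C global score whatever the observed distribution. In SAP 8.1, delete the clause that gives the non-parametric result primary status. Name one rank analysis as a pre-specified sensitivity analysis, either a van Elteren test or a rank ANCOVA with baseline RSS and age.

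If the sponsor wants to keep a switch, an acceptable form is one numeric cut-off on a stated type of ANCOVA residual, one named replacement test with its estimator, and a decision taken without arm labels before any treatment comparison is run.

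The cost is one clause and one sentence, and the sample size stays at 60. The sponsor gives up the option to switch. If scores prove heavily skewed, ANCOVA may be less powerful than a rank test, by about 6 points in the poor-responder scenario above (67.5% against 73.7%).

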8.2 Subject Accountability

The number and percentage of subjects in each of the analysis populations (Screened, Full, PK and PD) will be summarized by treatment group. Subjects and their data excluded from any analysis set will be listed.

Screen-failure subjects (ie, subjects screened but not randomized) and the associated reasons for failure to randomize will be tabulated overall for the Screened Population. The number and percentage of subjects who complete the treatment period and of subjects who prematurely discontinue will be presented for each treatment group and pooled across treatment groups for the Full Analysis set. The reasons for premature discontinuation from treatment period as recorded on eCRFs will be summarized.

8.3 Protocol Deviations

Protocol deviations will be summarized by type in each treatment group for the Full Analysis set. All protocol deviations will be listed.

8.4 Investigational Product Administration

8.4.1 Extent of Exposure

Exposure duration to the investigational product for the full analysis set will be summarized for KRN23 therapy and the active control (oral phosphate/active vitamin D) separately.

The total dose and prescribed weight-based dose of KRN23 will be summarized for the KRN23 group. The dosing information for oral phosphate and active vitamin D medications will be provided for the active control group.

8.4.2 Measurement of Treatment Compliance

For KRN23 group, the number of dosing and cumulative dose per subject administered will be summarized. The number of missed dosing will also be summarized.

For active control group, the number of full days with missed oral phosphate or active vitamin D medication will be summarized. The main reason for missed medication will also be summarized.

Descriptive statistics for investigational product compliance will be presented by treatment group for the Full Analysis Set by study visit and overall 40 and 64-week treatment period.

8.4.3 Demographic and Baseline Characteristics

Demographic parameters (age, age subgroup of < 5 years vs ≥ 5 years, sex, race, ethnicity, region, weight, recumbent length/standing height, body mass index [BMI]) and other baseline characteristics (general and disease-specific medical history, conventional therapy duration, age when conventional therapy initiated, XLH treatment history, PHEX mutation, RSS scores, RSS total score subgroup of ≤ 2.5 vs > 2.5 , XLH biochemical parameters, renal ultrasound scores) will be summarized descriptively by treatment group on the Full Analysis Set.

8.4.4 Prior and Concomitant Medication

Prior medication is defined as any medication started before the date of the first dose of investigational product (medication start date prior to the first dose date).

Concomitant medication is defined as any medication taken on or after the date of the first dose of investigational product [medication end date on or after first dose date (or ongoing), and medication start date prior or on the last dose date]. Any concomitant medications started after the date of the last dose of investigational product will not be presented in the summary tables but will be included in the subject data listings.

Baseline medication is defined as any medication taken on the first dose date [medication end date on or after first dose date (or ongoing), and medication start date prior or on the first dose date].

Both prior and concomitant medications will be coded by drug name and therapeutic class using WHO Drug Dictionary. If a subject took a specific medication multiple times or took multiple medications within a specific therapeutic class, that subject will be counted only once for the coded drug name or therapeutic class.

8.5 Efficacy Analysis

The efficacy analyses will be based on the Full Analysis Set.

8.5.1 Generalized Estimating Equations Model (GEE)

For repeated measures such as clinical outcomes, the GEE approach will be used for assessing the change over time. The GEE model will include treatment group, study visit and interaction between treatment group and study visit as categorical variables, stratification factors of baseline RSS total score and age will also be included, unless specified otherwise. To model the covariance structure, the exchangeable covariance matrix will be selected initially. If the exchangeable covariance structure leads to non-convergence, independence covariance structure will be applied. Model based estimates of the changes from baseline, SE and corresponding 95% confidence intervals (CIs) will also be provided along with P- values for assessing statistical significance. Other independent variables will be specified in the analysis section for each individual endpoints.

8.5.2 Sensitivity Analysis for Missing Data

Sensitivity analyses to assess the robustness of the primary analysis result to missing data will be conducted on RSS and RGI-C endpoints. Theses may include, but are not limited to:

- Last Observation Carried Forward (LOCF): the last non-missing post-baseline observation will be carried forward to the corresponding endpoint for evaluation. If no post-baseline observation is available, the baseline observation will be used for evaluation; if no baseline is available, the LOCF approach will not be performed.
- Multiple imputation (MI): the PROC MI procedure in SAS will be utilized to impute missing values using a Markov Chain Monte Carlo (MCMC) approach by 100 times. The imputed dataset will be analyzed by the ANCOVA model at Week 40 analysis or GEE model at Week 64 analysis, the results will be combined using the PROC MIANALYZE procedure in SAS. Baseline RSS total score, treatment group and baseline age stratification factor will be used as predictor variables in the imputation. Other variables such as change from baseline in ALP may also be considered as a predictor variable.

8.5.3 Analysis of Primary Efficacy Endpoint

The primary efficacy endpoint will be tested to compare the mean RGI-C global score between the KRN23 and active control groups.

At Week 40 analysis, an Analysis of Covariance (ANCOVA) model will be applied on the RGI-C global score with treatment group and baseline age stratification factor as independent variables, baseline RSS total score as a continuous covariate. The stratification factor of baseline RSS total score will not be included in the model.

For RGI-C knee, wrist and lower limb deformity scores, a similar ANCOVA model will be applied with baseline RSS wrist score used in RGI-C wrist score modeling and baseline RSS knee score used in RGI-C knee score and lower limb deformity score modeling.

At Week 64 analysis, RGI-C (global, knee, wrist and long leg) scores over time including Week 40 will be analyzed using GEE model that includes treatment group, visit, treatment group by visit interaction, baseline age stratification factor as independent variables, baseline RSS total score as a continuous covariate. The stratification factor of baseline RSS total score will not be included in the model.

The estimated difference of RGI-C between KRN23 treatment and active control group will be provided along with 95% CI and p-value. The estimated RGI-C score and its 95% CI within individual treatment groups will also be provided. Descriptive statistics for all RGI-C scores will be provided in both continuous and categorical summary. Summary of abnormality at baseline and change in abnormality at Week 40 and Week 64 will also be provided. A listing of RGI-C scores will be provided for each subject. Graphic displays of RGI-C scores will also be provided over time by treatment group.

If subjects receive orthopedic surgeries before week 40 X-ray visit, a sensitivity analysis will be performed by excluding these subjects from week 40 and week 64 RGI-C analyses. If subjects receive orthopedic surgery after week 40 but before week 64 X-ray visit, a sensitivity analysis will be performed at week 64 RGI-C analysis, where the week 40 RGI-C data will be used to impute Week 64 data for these subjects.

